TITLE	A Comparative Effectiveness Study of Peer Mentoring [PM] versus Structured Transition Education Based Intervention [STE] for the Management of Care Transitions in Emerging Adults with Sickle Cell Disease (SCD)
STUDY POPULATION	Emerging Adults with Sickle Cell Disease aged 16 – 25 years
SUMMARY OF STUDY RATIONALE	Emerging adults with sickle cell disease (EA-SCD) experience significant difficulties with transition from pediatrics to adult care despite the impressive gains in childhood survival. Acute care utilization dramatically increases, and quality of life drops along with an increased mortality. There is currently no clinical practice standard for transition programming for EA-SCD. Recently Got Transition Center for Healthcare Transition Improvement recommended an approach that involves incorporating the Six Core Elements of Transition into clinical practices that provide care for children with special healthcare needs (CSHCN) as noted in www.gottransition.org. The American Academy of Pediatrics (AAP) in partnership with the American Academy of Family Physicians (AAFP) and the American College of Physicians (ACP) proposed these Six Core Elements in 2011 in a consensus statement that provided clear guidance and a supportive decision algorithm that describes six practice-based recommendations (Fig. 4); 1: transition policy, 2: transition youth registry, 3: transition preparation, 4: transition planning, 5: transition and transfer of care, and 6: transition completion that should be a part of ANY planned health care transition program for all CSHCN. They based these recommendations on the premise that optimal health care is achieved when individuals of all ages receive "medically and developmentally appropriate care" in a process that includes ensuring that high-quality, developmentally appropriate health care services are available uninterrupted as the person moves from adolescence to adulthood." This project seeks to establish the comparative effectiveness of adding peer mentoring to a structured education-based transition program to improve self-care skills among EA-SCD. The peer mentoring comparator was chosen based on existing evidence of its utility in improving transition outcomes in other chronic diseases of childhood such as juvenile diabetes and solid organ transplant. We will test the hypothesis that th
	substantive quantative information to evaluate the 5151-of study s

	process outcomes, quality improvement, and impact through eliciting descriptions of participant experiences with one-to-one peer mentoring since we are unable to quantitatively assess the Standard Education + Peer Mentoring comparator as originally planned within the ST3P-UP Study.
STUDY DESIGN	This is a cluster randomized study comparing the effectiveness of adding virtual peer mentoring to a structured education-based transition program based on the Six Core Elements of transition in improving acute care reliance, quality of life and satisfaction with transition process in EASCD. The study will involve 14 clinical sites with a 1:1 randomization at the site level. A total of 537 EA-SCD between the ages of 16 and 25 years who are currently receiving care in a pediatric SCD program will be enrolled and followed prospectively for at least 6 months in pediatrics and at least 24 months in adult care. We will use rapid cycle PDSA improvement methods to implement the structured education-based program in adherence to the 6 core elements and measure adherence to these practice guidelines over time.
OBJECTIVES	 Primary Objective: Compare the effectiveness of STE+PM versus STE at decreasing the number of acute care visits per year over a 24-month period among EA-SCD. Secondary Objectives: To compare the effectiveness of STE+PM versus STE at improving patient- reported outcomes (PROs) among EA-SCD. To compare the effectiveness of STE+PM versus STE at reducing healthcare utilization among EA-SCD.
	 Qualitative Objectives: Identify the facilitators and barriers to enrollment of EA-SCD and mentors from multi stakeholder perspectives Assess mentor-mentee experiences with one-to-one peer mentoring Assess site experiences with the implementation of Quality Improvement methods within their clinical practices Determine the effect of engagement activities on communication within the site triad (adult/pediatric physicians, CBOs, patients) Develop a definition of transition success across the triad (adult/pediatric physicians, CBOs, and patients)
KEY INCLUSION CRITERIA	 Any Sickle Cell Disease genotype Age 16 – 25 years receiving care in a pediatric sickle cell program Able to complete all study procedures with reasonable accommodations

[figure not shown]
STATISTICAL CONSIDERATIONS	Estimated average acute care utilization rate for EA-SCD is 6 visits / year. This study is designed to detect a 20% reduction in the number of acute care encounters per year which is considered clinically significant to our patient stakeholders. Based on a two- sided alpha = 0.05 significance level, 67 subjects per arm would provide approximately 85% power to detect a 20% reduction in the number of acute care utilizations under individual randomization, assuming the number of encounters follows a Poisson distribution for rare events. Sample size was inflated based on the cluster size coefficient of variation among our 14 participating clinical sites (55%) and the intra-class correlation (ICC) assumed to be 0.05. Based on these parameters, 183 subjects per arm (366 total subjects) will retain approximately 85% power. The sample size was increased to 537 total EA-SCD subjects to account for potential missing data and allow for robust evaluation of secondary endpoints. It is estimated that this can be accomplished with an enrollment rate of 35% of the EA-SCD patient population.
NUMBER OF EA-SCD PARTICIPANTS	537 total participants will be enrolled Each arm will enroll approximately 269 EA-SCD aged 16 – 25 years
NUMBER OF CLUSTERS	There will be 14 cluster sites, each cluster site comprised of a pediatric SCD clinic, an adult SCD clinic and a SCD CBO. There are 8 large cluster sites with ≥40 EA-SCD currently in pediatrics and 6 small cluster sites with <40 EA-SCD currently in pediatric care. Based on self-reported enrollment targets from each site, 80% of participants will come from large clusters.

SCHEMA

[figure not shown]
Study Schema Figure 1: Overview of Study Design

	Study Schema										
Practices with Emerging Adults with SCD (EA-SCD) aged 16 - 25y Randomized at the Practice Level											
Small Sized Program [≤ 40 EA-SCD] Large Sized Program [> 40 EA-SCD]											
Arm 1- A	Arm 1- B	Arm 2-A	Arm 2-B								
Structured Education Based Transition Program [STE]	Structured Education Based Transition Program [STE] + Peer Mentoring [STE + PM]	Structured Education Based Transition Program [STE]	Structured Education Based Transition Program [STE] + Peer Mentoring [STE + PM]								
	Outcome Meas	ures at 24 Montl	ns								
Primary Outcome: Cha		are visits [ED visits, Adm Hospital Days]	issions, Readmissions at 14d,								
Secondary Outcome: Change in patient reported outcomes (MOS-SS, TIP-RFT, PedsQL-SCD, ASCQ-Me QOC], Satisfaction with Transition Process, Change in Ambulatory Care visits											
Process Outcome: Chang	ge in Adherence to Standa	rd Transition process, T	ransition Feedback survey								

Study Schema Figure 2: Overview of Study Implementation Outline

Study Schema Figure 3: Peer Mentoring Impact on Clinical Outcomes

GLOSSARY OF TERMS

ACR	Acute Care Reliance								
ASCQ-ME	Adults Sickle Cell Quality of Life Measure								
CAB	Community Advisory Board								
CBO	Community-Based Organization								
CHW	Community Health Workers								
CSHCN	Children with Special Healthcare Needs								
DCC	Data Coordinating Center								
DSMC	Data Safety Monitoring Council								
EA	Emerging Adult								
EA-SCD	Emerging Adult with Sickle Cell Disease								
ED	Emergency Department								
HBCU	Historically Black Colleges and Universities								
HCT	Healthcare Transition								
Hgb	Hemoglobin								
IRB	Institutional Review Board								
MOS-SSS	Medical Outcomes Study Social Support Survey								
PDSA	Plan – Do – Study – Act								
$PedsQL^{TM}$	Pediatric Quality of Life								
PM	Peer Mentoring								
PRO	Patient Reported Outcomes								
QI	Quality Improvement								
QI Coordinator	Quality Improvement Coordinator								
QOL	Quality of Life								
SAC	Study Advisory Committee								
SCD	Sickle Cell Disease								
FSCDQ	"How Much Do I Know about SCD" Quiz								
SE US	Southeastern United States								
SOG	Study Oversight Group								
STE	Structured Education-Based Transition Program								

TABLE OF CONTENTS

SYN	OPSIS	I
SCH	IEMA	IV
1.	BACKGROUND AND RATIONALE	9
1.1	Background	
1.2	Study Rationale and Study Design	11
2.	STUDY OBJECTIVES	14
2.1	Primary Objective	
2.2	Secondary Objectives	14
2.3	Exploratory Objectives	
2.4	Qualitative Research Objectives	15
3.	SUBJECT SELECTION	16
3.1	Subject Identification and Recruitment	
3.2	EA-SCD Eligibility	
3.3	Mentor Eligibility	
3.4	Advisor Eligibility	
3.5	Qualitative Research Eligibility	
3.6	Screen Failures	19
4.	REGISTRATION AND RANDOMIZATION	
4.1	Study ID Number Assignment	
4.2	Randomization Method and Stratification Factors	19
5.	STUDY PLAN	
5.1	Study Intervention	
5.2	Procedures for Standardizing PM Implementation at Each Site	
5.3	Study Outcome Measures	27
6.	STUDY CALENDAR	
6.1	Site Level Quality Improvement Calendar	
6.2	Site Level Advisor/Mentor Calendar	

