2. STUDY OBJECTIVES

2.1 Primary Objective

The primary objective of this study is to compare the effectiveness of STE+PM versus STE at decreasing the number of acute care visits per year over a 24-month period among EA-SCD.

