10.2 Sample Size and Accrual

Sample size calculations are based on the primary endpoint of acute care utilization visits per year (at the EA-SCD participant level). Utilizing a randomized cluster design, seven clinical sites will be randomized per arm. The sample size calculation strategy is to calculate the required minimum sample size based on an individual patient randomized design, and then inflate the sample size based on cluster randomized considerations.⁵⁴ A conservative estimate of the average acute care utilization rate for EA-SCD is 6 acute care visits per year based on data for North Carolina reported by the RuSH population surveillance project.⁴ In South Carolina, the acute care utilization rates among 18-30 y with SCD was reported as 7.17 (95% CI 6.34-7.99).55 At Atrium Health (formerly known as Carolinas Healthcare System), 295 EA-SCD had 1972 emergency department visits and 221 hospital admissions in 2015 with an average acute care

utilization rate of 6.82 visits per year. This study is designed to detect a 20% reduction in the number of acute care encounters per year (assuming a base case of 6 encounters). A 20% reduction in acute care utilization is considered clinically significant based on patient partners reporting that 1 less acute care visit a year is meaningful. Based on a two- sided alpha = 0.05significance level, 67 EA-SCD participants per arm would provide approximately 85% power to detect a 20% reduction in the number of acute care utilizations under individual randomization, assuming the number of encounters follows a Poisson distribution for rare events. The sample size will be inflated based on two parameters: the cluster size coefficient of variation and the intra-class correlation (ICC).⁵⁴ The cluster size coefficient of variation observed among the 14 participating clinical sites is 55%. Therefore, the coefficient of variation is assumed to be 60% and the ICC is assumed to be 0.05.⁵⁶ Based on these parameters, a minimum of 183 EA-SCD participants per arm (366 total EA-SCD participants) will retain approximately 85% power. To account for potential missing data and allow for robust evaluation of secondary endpoints the sample size will be increased to a total of 537 EA-SCD participants. It is estimated that this enrollment can be accomplished with an enrollment rate of 35% of the EA-SCD patient population.

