10.5.4 Primary Analysis

To evaluate the impact of PM, the acute care utilization rate per year will be compared between the PM+STE and STE arms. This will be accomplished using generalized linear mixed model with a Poisson distribution-log link construct. The model will include fixed effects for baseline acute care visits per year, the stratification factor (large sites vs small sites) and treatment arm, and a random effect for clinical site. Corresponding 95% confidence intervals will be calculated for the estimated ACU rate in each treatment arm.

Supportive and sensitivity analyses will be conducted to include potential confounding factors such as urban versus rural sites, education level, older first degree relative with SCD, genotype, age at transfer to adult care, and type of receiving provider (primary versus specialty). Univariate models will be fit for each factor, and those identified to be individually prognostic will be included in a multivariable model, and backward elimination followed by forward selection will be used to identify factors that are independently prognostic and to establish a final base model. Finally, treatment arm will be added to the base model to evaluate the impact of the intervention adjusting for significant baseline factors.

Two analyses will be conducted to estimate the impact of differential accrual between arms over time: (1) An additional term of year of enrollment will be added to the GLMM as a categorical variable; (2) We will subset the analyses to EA-SCD who were contemporaneously enrolled. Comparison of the PM+STE and STE ACU estimates from this subset to those results including all enrolled with and without controlling for year of enrollment will provide a comprehensive assessment of the potential bias due to differential accrual between arms over time. ACU rate in the STE only arm will be compared to historical ACU rates which were used for the original power calculations. Although these are comparisons to historical controls, this will provide preliminary evidence using a robust sample size of the potential impact of the structure transition education.

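### The synopsis says the peer mentoring comparator cannot be quantitatively assessed as first planned, but the power statement and the status of the primary comparison stand unrevised

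*Combined protocol and SAP*

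**What the plan says.** The summary of study rationale in the synopsis ends by explaining why qualitative aims were added: "since we are unable to quantitatively assess the Standard Education + Peer Mentoring comparator as originally planned within the ST3P-UP Study". This is current Version 6 text, not a change log.

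The rest of the document keeps the quantitative comparison in place:

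- Section 2.1 sets the primary objective: to "compare the effectiveness of STE+PM versus STE at decreasing the number of acute care visits per year over a 24-month period among EA-SCD".
- The statistical considerations in the synopsis start from individual randomization: "Based on a two- sided alpha = 0.05 significance level, 67 subjects per arm would provide approximately 85% power". They then inflate for clustering to 183 per arm and raise the total to 537. The synopsis row on participant numbers gives about 269 per arm, and that figure appears nowhere else.
- Section 10.2 repeats the calculation and concludes that "a minimum of 183 EA-SCD participants per arm (366 total EA-SCD participants) will retain approximately 85% power".
- Section 10.5.4 defines the primary analysis as a Poisson mixed model in which "the acute care utilization rate per year will be compared between the PM+STE and STE arms".

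Section 10.5.4 also plans two analyses for differential accrual between arms over time, and compares the STE arm with historical rates. Section 1.2 describes the qualitative aims as supplementing the study's original aims. Neither section revises the sample size or the power, or changes the standing of the primary comparison.

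**The concern.** One part of the protocol reports a limitation on assessing the intervention arm quantitatively. The parts that define what the trial can conclude do not mention it. A reader of section 10.2 alone would take the comparison to have about 85% power for a 20% reduction. A reader of the synopsis would not know whether that still holds.

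What is at stake is how the primary result will be read. If the PM arm ends up small, a non-significant result set against a stated 85% power invites the conclusion that peer mentoring does not work, when the data may be too imprecise to say so. If the status of the comparison is left open, it could also be settled after the results are known.

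**Working it through.** **Inputs.** All are from section 10.2 unless noted: control rate 6 visits per year; 20% reduction, so 4.8 in the PM arm; two-sided alpha 0.05; Poisson counts (variance equals mean); seven sites per arm; ICC 0.05; cluster-size coefficient of variation (CV) 60%; about 269 per arm (synopsis). One year of exposure is used because this reproduces the plan's figures.

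**Step 1: individual randomization.** n = (1.960 + 1.036)² × (6 + 4.8) / (6 − 4.8)² = 8.978 × 10.8 / 1.44 = 67.3. The plan's 67 is reproduced.

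**Step 2: cluster inflation with a fixed number of sites.** With k = 7 and design effect DE = 1 + [(1 + CV²)·N/k − 1]·ICC for N participants in an arm, the required number is

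N = k·n·(1 − ICC) / [k − n·ICC·(1 + CV²)] = 7 × 67 × 0.95 / (7 − 67 × 0.05 × 1.36) = 182.3, rounded up to 183.

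The plan's 183 is reproduced. It needs the 60% CV of section 10.2. The synopsis names only the observed 55%, which gives 169.

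**Step 3: power at 183 per arm.** DE = 1 + (1.36 × 183/7 − 1) × 0.05 = 2.73. Effective size = 183/2.73 = 67.1. Power = Φ(1.2/√(10.8/67.1) − 1.96) = 84.9%. The stated power is therefore correct for its inputs, which are two equal arms with at least 183 each.

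**Step 4: power if the PM arm is smaller.** No PM enrolment figure is given, so the PM numbers below are assumptions. STE is held at 269 (DE 3.56, effective size 75.5) and seven sites per arm are kept. With e the effective size:

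Power = Φ(1.2 / √(6/e_STE + 4.8/e_PM) − 1.96)

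The last column is the 95% CI around an observed rate ratio of 0.80, computed as 0.80 × exp(±1.96 × √[1/(6·e_STE) + 1/(4.8·e_PM)]).

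| PM participants | DE | Effective size | Power | 95% CI at ratio 0.80 |
|---|---|---|---|---|
| 269 | 3.56 | 75.5 | 88.7% | 0.70 to 0.92 |
| 134 | 2.25 | 59.5 | 85.0% | 0.69 to 0.93 |
| 100 | 1.92 | 52.0 | 82.5% | 0.69 to 0.93 |
| 50 | 1.44 | 34.8 | 73.0% | 0.67 to 0.96 |
| 25 | 1.19 | 21.0 | 57.9% | 0.64 to 0.99 |

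On the plan's assumptions the PM arm could fall to about half its target before power drops below 85%, because clustering already limits what extra participants per site contribute. Below about 100 the loss becomes material.

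**The case against.** The best defence is the qualifier in the synopsis clause. Being unable to assess the comparator as first planned is compatible with still running the two-arm model, perhaps with fewer or later PM participants. Section 1.2 supports this by calling the qualitative aims supplementary. The text just before the clause is not legible in the copy available, and the reason and extent of the problem may have been given there. A design-stage sample size is also properly kept as a record. All of this stands.

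Three stronger readings are therefore not supported:

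- **That the two statements cannot both be true, or that the comparison has been abandoned.** The qualifier leaves room for a modified comparison.
- **That the protocol admits to lost power or an under-enrolled PM arm.** The clause mentions neither. Some provisions suggest accrual difficulty: the differential-accrual analyses, reconsent after delayed matching at PM sites (section 3.2.1), PM enrolment only after a mentor match (section 10.1.2), and the aim on enrolment barriers (section 2.4). That remains an inference.
- **That power is really around 10%.** Such a figure comes from using the single-system mean and SD of 4.2 ± 6.8 for ages 19 to 21 (section 1.1) as the variance. With variance ratio 6.8²/4.2 = 11.0, power is Φ(0.84/√(11.0 × 7.56/75.5) − 1.96), about 12%, even at 269 versus 269. This ignores the baseline-visits covariate. It is a question about overdispersion, not a consequence of PM enrolment.

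It can also be said that section 10.5.4 already deals with the problem. Its year-of-enrolment term and contemporaneous subset address bias from uneven accrual. They do not update power or precision, or say how a null result will be read.

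**Conclusion.** The point holds as an unreconciled inconsistency about the primary comparison. The synopsis qualifies whether the PM comparator can be assessed, while the synopsis statistics and section 10.2 keep the design power without comment, and sections 2.1 and 10.5.4 keep the comparison's primary status without comment. The arithmetic behind 67 and 183 per arm is correct.

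The size of any loss cannot be determined from the documents. It ranges from none (PM enrolment of about 134 or more against 269 STE participants) to a power of about 58% at 25 PM participants. This rests on the plan's Poisson variance, ICC 0.05, CV 60%, seven contributing sites in each arm, a full STE arm, no allowance for missing data, and a normal reference distribution. With only 14 sites, a t reference on 12 degrees of freedom lowers the starting point (78% at 183 per arm, 83% at 268.5 per arm), so the 134 threshold applies only to the plan's own method.

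**What to change.** 1. In the synopsis statistics and section 10.2, keep the original calculation and label it as the design-stage record. Add the expected enrolment in each arm, and the power or the 95% CI width for the rate ratio at those numbers.
2. In sections 2.1 and 10.5.4, state before the final analysis whether STE+PM versus STE remains confirmatory or is for estimation. If the updated power falls short of 85%, commit to reporting the rate ratio with its 95% CI and to not reading non-significance as absence of effect.
3. Reword the synopsis sentence so that it says what can no longer be assessed as planned and what still will be, consistent with those sections.

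The cost is wording and one recalculation from enrolment figures the sponsor should hold. The stated power may become less favourable. No additional participants or procedures are needed.

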1. BACKGROUND AND RATIONALE

1.1 Background

Nearly 100,000 individuals are living with sickle cell disease (SCD) in the United States (US), 60% are adults (\geq 18y) and a third are emerging adults (16-25y; EA-SCD). ¹⁻⁴ The disease predominantly affects minorities with over 30% residing in the region planned for this intervention (southeastern [SE] US).² SCD is characterized by a spectrum of symptoms and complications, including periods of unpredictable acute pain, debilitating chronic pain, multi-organ injury, reduced quality of life (QOL), and shortened lifespan.^{2,5} Over 95% of children with SCD will survive into adulthood, due to early diagnosis, innovative preventative therapies, and improved comprehensive care. 6 Unfortunately, mortality rates continue to rise for adults with SCD, in part due to a dire lack of access to high-quality care for the influx of EA-SCD who are surviving into adulthood. Healthcare systems have not adjusted to the shifting epidemiology of SCD in adults that need complex care coordination and support to optimally manage the medical and psychosocial comorbidities that increase with age.⁸ While the mortality rates among children with SCD have declined ~3\% per year between 1979 to 2005, there has been a steady 1\% per year increase in adult mortality rates.⁷ Median life expectancy for individuals with SCD in the US in the 1990s ranged between 42-48 years for hemoglobin SS (Hgb SS) and 60-68 years for hemoglobin SC (Hgb SC). A more recent population-based SCD surveillance report from CA and GA cites tripling of all-cause mortality rates amongst 15-24 year olds (y) compared to those under age 14.10 All-cause mortality rates remain higher for SCD compared to all African Americans (AA) and the general US population.¹⁰

Transition from pediatrics to adult care is a critical time for EA-SCD. The emergency department (ED) becomes a primary source for care, with ED visits and admissions per year doubling, and avoidable acute care visits rising to account for two-thirds of all SCD hospitalizations. ^{8,11,12} Data from the Healthcare Cost and Utilization Project State Inpatient Databases and State Emergency Department Databases from eight states showed that EA-SCD (18–30y) had the highest acute care utilization rates compared to children 10-17y (3.61 vs 2.04 visits/patient/year). ¹³ The 30-day readmission rate doubled from 27.4% to 48.9% respectively. ¹³ Data from the Registry and Surveillance for Hemoglobinopathies (RuSH) Project cite an increase in acute care utilization rates among EA-SCD (Fig 1). In GA, utilization rose from 0.8 to 3.0/person/year among individuals 10-19y of age compared to those 20 - 49y. ¹⁴ In NC, the average annual acute care visits per person increased from 5 in those <18 years to 12 among 18-35y. ⁴ Disparities also exist with school absenteeism, and EA-SCD miss an average of 20-40 school days/year due to illness, have worse standardized test scores, higher rates of repeat grades and lower overall school attainment compared to controls. ¹⁵ There is limited research to support evidence-based interventions that effectively reduce the high mortality, morbidity, and poor QOL during transition.

Barriers to Transition:

Several identified patient, provider and health system factors contribute to the poor health outcomes of EA-SCD during transition. ¹⁶⁻¹⁸ EA-SCD struggle emotionally with adjusting from a more paternalistic pediatric model to the adult "individualistic" model of care. Adherence to disease modifying treatment drops significantly as they struggle with the developmental maturation process. ¹⁹ Changes or lapses in insurance lead to gaps in comprehensive care -

Version 6: 12/22/2022

specialized and primary - during transition, amplifying existing barriers to accessing crucial services as disease burden is increasing. 20,21 A retrospective study showed that patients who are transitioning received 46% fewer transfusions by age 22y compared to children and were 4.7 times less likely to receive iron chelation by age 25y. 21 At Atrium Health (formerly known as Carolinas Healthcare System), a large healthcare system in the SE US that provides care for 1300 adults and 400 children with SCD, only 8-14% of EA-SCD accessed a scheduled visit with their primary care/SCD provider in 2015 with mean acute care reliance (ACR; number of acute care visits per year/ [all acute care visits + all ambulatory care visits]) rates of 42% (Fig 2). Mean acute care visits/year rose significantly from 2.1 ± 2.9 among 16- 18y to 4.2 ± 6.8 among 19 - 21y and was highest among 21 - 25y at 5.3 ± 8.5 (p<0.01). ACR (\geq 0.33) is an indicator of inadequate access to primary and preventative care. 22 EA-SCD report having inadequate information about adult care and a poor understanding of their disease and how it becomes more complex with age. $^{14, 16}$ There are significant knowledge gaps and poor communication between pediatric and adult providers that worsen the problem created by a lack of standardized EA-SCD patient education curriculum.

Limited evidence on effective transition programming:

A population-based approach to care coordination provided through effective and culturally acceptable delivery models during and after the transition is essential to reduce the unacceptable morbidity and mortality of EA-SCD. Healthcare transition refers to "the purposeful and planned movement of adolescents and young adults with chronic physical and medical conditions from child- centered to adult-oriented health care systems". ²³ A planned and structured transition process will maximize lifelong functioning and well-being, optimize health and assist EA-SCDs in reaching their full potential by providing support in acquiring independent health care and life skills, preparing for the differences in an adult model of care, and transferring successfully to new adult providers without disruptions in care. Transition planning that involves engagement between EAs, their caregivers and providers has been shown to lead to improvements in adherence to, continuity with, and overall satisfaction with healthcare. 11,24 When transition education is targeted and structured there is increased probability of achieving independent self-care among EA-SCD.²⁵ A recent report on the state of transition practices for children with special health care needs (CSHCN) revealed a lack of established best practices for EA transition, with only 25 programs nationwide that evaluated transition care in juvenile diabetes, SCD, solid organ transplant and other chronic childhood conditions.²⁶ Education-based interventions, use of a multidisciplinary team and a transition coordinator were common themes. Most programs evaluated disease status, adherence to adult appointments or medical regimen and patient satisfaction. A study by Maslow et al included a structured mentoring program showing improved self-efficacy and transition readiness among participants.²⁷ Only two studies were randomized trials, and none had a concurrent comparison group. The review highlighted the need for further prospective studies with concurrent comparison groups utilizing well-defined transition outcomes to measure the entire transition process. Additional evidence gaps identified include the need to involve health systems in the transition process, have longer follow up (> 1y), increase use of Quality Improvement (QI) initiatives to help identify best practices and overcome the challenges with patient level randomization, and use of validated tools to assess patient reported outcomes (PROs). Patient education was common to all 25 identified transition programs; therefore, our choice for a standard comparative transition model for this proposal will evaluate an education-based, structured transition program that utilizes a QI approach to standardize the transition process across clinical sites and integrate this into routine care for all EA-SCD.
